12 REGISTRATION GUIDELINES

Once signed, informed consent has been obtained; patients will be entered on study. To register a patient, the data manager must complete the Eligibility Checklist (**Appendix B**). The data coordinator will register the patient onto the study and assign a unique patient number.

13 DATA SUBMISSION

13.1 Confidentiality of Records

Information about study subjects will be kept confidential and managed according to the requirements of the Health Insurance Portability and Accountability Act (HIPAA). Those regulations require a signed subject authorization informing the subject of the following:

- What protected health information (PHI) will be collected from subjects in this study
- Who will have access to that information and why
- Who will use or disclose that information
- The rights of a research subject to revoke their authorization for use of their PHI.

In the event that a subject revokes authorization to collect or use PHI, the investigator, by regulation, retains the ability to use all information collected prior to the revocation of subject authorization. For subjects that have revoked authorization to collect or use PHI, attempts should be made to obtain permission to collect at least vital status (i.e. that the subject is alive) at the end of their scheduled study period.

The data collection system (eVELOS) for this study uses built-in security features to encrypt all data, preventing unauthorized access to confidential participant information. Access to the system is controlled by a sequence of individually assigned user identification codes and passwords, made available only to authorized personnel who have completed prerequisite training.

13.2 Patient Consent Form

At the time of registration, three signed and dated copies of the patient Informed Consent form with the Human Rights must be available (for patient, patient's medical chart and one for UC Davis).

13.3 Registration Eligibility Worksheet

At the time of registration, the information requested on Eligibility Checklist will be submitted to the Protocol Coordinator.

13.4 Data Collection Forms and Submission Schedule

All data will be collected using the UCD Database System (eVELOS) forms. All data forms will be completed, submitted and processed in accordance with UCD CTSU policies.

13.5 Database Management and Quality Control

Quality assurance audits of select patients and source documents may be conducted by the UC Davis Cancer Center Quality Assurance Committee as outlined in the UC Davis Cancer Center Data and Safety Monitoring plan.

Quality control will be maintained by the CTSU Quality Assurance team according to CTSU policy.

14 MINORITIES AND WOMEN STATEMENT

Recruitment is open to all minorities. Although distributions may vary by disease type, our recruitment procedures have been developed to enroll patients who are representative of the respective target population.

15 ETHICAL AND REGULATORY CONSIDERATIONS

15.1 Ethical Conduct of the Study

This study will be conducted in accordance with the Declaration of Helsinki and Good Clinical Practice (GCP) according to (International Conference on Harmonization) ICH guidelines. Specifically, the study will be conducted under a protocol reviewed by an IRB; the study will be conducted by scientifically and medically qualified persons; the benefits of the study are in proportion to the risks; the rights and welfare of the subjects will be respected; the physicians conducting the study do not find the hazards to outweigh the potential benefits; and each subject will give his or her written, informed consent before any protocol-driven tests or evaluations are performed.

Essential clinical documents will be maintained to demonstrate the validity of the study and the integrity of the data collected. Master files will be established at the beginning of the study, maintained for the duration of the study and retained according to the appropriate regulations.

15.2 Informed Consent Procedures

Informed consent will be obtained before conducting any study-specific procedures (i.e. all of the procedures described in the protocol). The process of obtaining informed consent will be documented in the patient source documents.

All patients will have signed an informed consent for participation in research activities in accord with all institutional, NCI and Federal regulations, and will have been given a copy of the Experimental Subject's Bill of Rights.

16 DATA AND SAFETY MONITORING

This protocol is also subject to the UC Davis Cancer Center's (UCDCC) Data and Safety Monitoring Plan. The UCDCC is committed to pursuing high-quality patient-oriented clinical research and has established mechanisms to ensure both scientific rigor and patient safety in the conduct of clinical research studies. The UCDCC relies on a multi-tiered committee system that reviews and monitors all cancer clinical trials and ensures the safety of its participants, in compliance with institutional and federal requirements on adverse event (AE) reporting, verification of data accuracy, and adherence to protocol eligibility requirements, treatment guidelines, and related matters. The Scientific Review Committee (SRC) assumes overall oversight of cancer studies, with assistance and input from two independent, but interacting, committees: the Quality Assurance Committee and the Data Safety Monitoring Committee. A multi-level review system strengthens the ability of the UCDCC to fulfill its mission in conducting high quality clinical cancer research.

As per University of California Davis Cancer Center (UCDCC) Clinical Trials Support Unit (CTSU) SOP AM 506: Protocol Specific Meetings, the principal investigator (PI), clinical research coordinator (CRC), and the clinical research nurse meet at least monthly for ongoing study information, to discuss patient data and adverse events and to determine if dose escalation is warranted, when applicable.

According to the UCDCC Data and Safety Monitoring Plan (DSMP), any new serious adverse events related to the drugs being used on this trial are reviewed monthly by the UCDCC Data and Safety Monitoring Committee (DSMC) and any applicable changes to the study are recommended to the PI, if necessary.

The UCDCC Scientific Review Committee (SRC) determines if a UCDCC Data and Safety Monitoring Board (DSMB) is required. If required, the DSMC will appoint a DSMB. The DSMB is responsible for reviewing study accrual logs, adverse event information and dose escalation meeting minutes (where applicable) to ensure subject safety and compliance with protocol defined guidelines.

17 PATHOLOGY REVIEW

All patients will have malignancy confirmed by review of their biopsy specimens by the Department of Pathology at the University of California at Davis.

19 APPENDIX
Appendix A – ECOG/Zubrod Performance Status Scale

ECOG/Zubrod Performance Status Scale		Karnofsky Performance Scale	
Grade	Descriptions	Percent	Description
0	Normal activity. Fully active, able to carry on all pre-disease performance without restriction.	100	Normal, no complaints, no evidence of disease.
		90	Able to carry on normal activity; minor signs or symptoms of disease.
1	Symptoms, but ambulatory. Restricted in physically strenuous activity, but ambulatory and able to carry out work of a light or sedentary nature (e.g., light housework, office work).	80	Normal activity with effort; some signs or symptoms of disease.
		70	Cares for self, unable to carry on normal activity or to do active work.
2	In bed <50% of the time. Ambulatory and capable of all self-care, but unable to carry out any work activities. Up and about more than 50% of waking hours.	60	Requires occasional assistance, but is able to care for most of his/her needs.
		50	Requires considerable assistance and frequent medical care.
3	In bed >50% of the time. Capable of only limited self-care, confined to bed or chair more than 50% of waking hours.	40	Disabled, requires special care and assistance.
		30	Severely disabled, hospitalization indicated. Death not imminent.
4	100% bedridden. Completely disabled. Cannot carry on any self-care. Totally confined to bed or chair.	20	Very sick, hospitalization indicated. Death not imminent.
		10	Moribund, fatal processes progressing rapidly.
5	Dead.	0	Dead.

Appendix B – Eligibility Worksheet

Patient Name _____ MRN _____

Each question must be answered appropriately for a patient to be considered eligible for registration. Patients are eligible if they meet the following criteria (all answers must be “yes”). If the criteria is not applicable answer “yes.”

YES	NO	CRITERIA
		Histologically or cytologically confirmed colon, rectal, pancreatic, gastroesophageal, appendiceal, or small bowel adenocarcinoma
		Intent to treat with a FOLFOX chemotherapy regimen containing oxaliplatin at 85 mg/m ² on an every 2 week basis.
		Prior radiation or surgery is allowed, but should be finished at least 2 weeks prior to study enrollment.
		18 years or older.
		Zubrod performance status equal to or less than 2. See Appendix A
		Life expectancy of at least 3 months.
		Absolute neutrophil count greater than or equal to 1,500/microL
		Platelets greater than or equal to 100,000/microL
		Total bilirubin less than 3 X institutional upper limit of normal (ULN)
		AST (SGOT) less than or equal to 5 X ULN
		Creatinine less than 1.5 X ULN
		Women of child bearing potential must not be pregnant. A pre-study pregnancy test must be negative.
		Women of child-bearing potential must agree to use adequate contraception (hormonal or barrier method of birth control; abstinence) prior to study entry and for 30 days after study participation.
		Men must agree to use adequate contraception (barrier method or abstinence) prior to study entry and for 30 days after study participation.
		Able to understand and willing to sign a written informed consent document.
		No prior oxaliplatin.
		No plans to receive concomitant radiation.
		No uncontrolled intercurrent illness including, but not limited to, ongoing or active infection, symptomatic congestive heart failure, unstable angina pectoris, cardiac arrhythmia, or psychiatric illness/social situations that would limit compliance with study requirements.
		Not allergic to any platinum agent.
		No more than Grade 1 peripheral neuropathy.

Eligibility Checklist Completed By: _____ Date: _____

Appendix C - Response Evaluation Criteria in Solid Tumors (RECIST) v. 1.1

Response and progression will be evaluated in this study using the international criteria proposed by the revised Response Evaluation Criteria in Solid Tumors (RECIST) guideline (version 1.1) [Eur J Ca 45:228-247, 2009]. Changes in the largest diameter (unidimensional measurement) of the tumor lesions and the shortest diameter in the case of malignant lymph nodes are used in the RECIST criteria.

Definitions

Evaluable for toxicity. All patients will be evaluable for toxicity from the time of their first administration of the [¹⁴C]oxaliplatin microdose.

Evaluable for objective response. Only those patients who have measurable disease present at baseline, have received at least one cycle of FOLFOX therapy, and have had their disease re-evaluated will be considered evaluable for response. These patients will have their response classified according to the definitions stated below. (Note: Patients who exhibit objective disease progression prior to the end of cycle 1 will also be considered evaluable.)

Evaluable Non-Target Disease Response. Patients who have lesions present at baseline that are evaluable but do not meet the definitions of measurable disease, have received at least one cycle of therapy, and have had their disease re-evaluated will be considered evaluable for non-target disease. The response assessment is based on the presence, absence, or unequivocal progression of the lesions.

Disease Parameters

Measurable disease. Measurable lesions are defined as those that can be accurately measured in at least one dimension (longest diameter to be recorded) as ≥ 20 mm by chest x-ray, as ≥ 10 mm with CT scan, or ≥ 10 mm with calipers by clinical exam. All tumor measurements must be recorded in millimeters (or decimal fractions of centimeters).

Note: Tumor lesions that are situated in a previously irradiated area are not considered measurable unless they have been demonstrated to progress prior to their selection as a measurable lesion for this study.

Malignant lymph nodes. To be considered pathologically enlarged and measurable, a lymph node must be ≥ 15 mm in short axis when assessed by CT scan (CT scan slice thickness recommended to be no greater than 5 mm). At baseline and in follow-up, only the short axis will be measured and followed.

Non-measurable disease. All other lesions (or sites of disease), including small lesions (longest diameter <10 mm or pathological lymph nodes with ≥ 10 to <15 mm short axis), are considered non-measurable disease. Bone lesions, leptomeningeal disease, ascites, pleural/pericardial effusions, lymphangitis cutis/pulmonitis, inflammatory breast

disease, and abdominal masses (not followed by CT or MRI), are considered as non-measurable.

Note: Cystic lesions that meet the criteria for radiographically defined simple cysts should not be considered as malignant lesions (neither measurable nor non-measurable) since they are, by definition, simple cysts.

'Cystic lesions' thought to represent cystic metastases can be considered as measurable lesions, if they meet the definition of measurability described above. However, if non-cystic lesions are present in the same patient, these are preferred for selection as target lesions.

Target lesions. All measurable lesions up to a maximum of 2 lesions per organ and 5 lesions in total, representative of all involved organs, should be identified as **target lesions** and recorded and measured at baseline. Target lesions should be selected on the basis of their size (lesions with the longest diameter), be representative of all involved organs, but in addition should be those that lend themselves to reproducible repeated measurements. It may be the case that, on occasion, the largest lesion does not lend itself to reproducible measurement in which circumstance the next largest lesion which can be measured reproducibly should be selected. A sum of the diameters (longest for non-nodal lesions, short axis for nodal lesions) for all target lesions will be calculated and reported as the baseline sum diameters. If lymph nodes are to be included in the sum, then only the short axis is added into the sum. The baseline sum diameters will be used as reference to further characterize any objective tumor regression in the measurable dimension of the disease.

Non-target lesions. All other lesions (or sites of disease) including any measurable lesions over and above the 5 target lesions should be identified as **non-target lesions** and should also be recorded at baseline. Measurements of these lesions are not required, but the presence, absence, or in rare cases unequivocal progression of each should be noted throughout follow-up.

Methods for Evaluation of Measurable Disease

All measurements should be taken and recorded in metric notation using a ruler or calipers. All baseline evaluations should be performed as closely as possible to the beginning of treatment and never more than 4 weeks before the beginning of the treatment.

The same method of assessment and the same technique should be used to characterize each identified and reported lesion at baseline and during follow-up. Imaging-based evaluation is preferred to evaluation by clinical examination unless the lesion(s) being followed cannot be imaged but are assessable by clinical exam.

Clinical lesions: Clinical lesions will only be considered measurable when they are superficial (e.g., skin nodules and palpable lymph nodes) and ≥ 10 mm diameter as assessed using calipers (e.g., skin nodules). In the case of skin lesions, documentation by color photography, including a ruler to estimate the size of the lesion, is recommended.

Chest x-ray: Lesions on chest x-ray are acceptable as measurable lesions when they are clearly defined and surrounded by aerated lung. However, CT is preferable.

Conventional CT and MRI: This guideline has defined measurability of lesions on CT scan based on the assumption that CT slice thickness is 5 mm or less. If CT scans have slice thickness greater than 5 mm, the minimum size for a measurable lesion should be twice the slice thickness. MRI is also acceptable in certain situations (e.g. for body scans).

Use of MRI remains a complex issue. MRI has excellent contrast, spatial, and temporal resolution; however, there are many image acquisition variables involved in MRI, which greatly impact image quality, lesion conspicuity, and measurement. Furthermore, the availability of MRI is variable globally. As with CT, if an MRI is performed, the technical specifications of the scanning sequences used should be optimized for the evaluation of the type and site of disease. Furthermore, as with CT, the modality used at follow-up should be the same as was used at baseline and the lesions should be measured/assessed on the same pulse sequence. It is beyond the scope of the RECIST guidelines to prescribe specific MRI pulse sequence parameters for all scanners, body parts, and diseases. Ideally, the same type of scanner should be used and the image acquisition protocol should be followed as closely as possible to prior scans. Body scans should be performed with breath-hold scanning techniques, if possible.

PET-CT: At present, the low dose or attenuation correction CT portion of a combined PET-CT is not always of optimal diagnostic CT quality for use with RECIST measurements. However, if the site can document that the CT performed as part of a PET-CT is of identical diagnostic quality to a diagnostic CT (with IV and oral contrast), then the CT portion of the PET-CT can be used for RECIST measurements and can be used interchangeably with conventional CT in accurately measuring cancer lesions over time. Note, however, that the PET portion of the CT introduces additional data which may bias an investigator if it is not routinely or serially performed.

Ultrasound: Ultrasound is not useful in assessment of lesion size and should not be used as a method of measurement. Ultrasound examinations cannot be reproduced in their entirety for independent review at a later date and, because they are operator dependent, it cannot be guaranteed that the same technique and measurements will be taken from one assessment to the next. If new lesions are identified by ultrasound in the course of the study, confirmation by CT or MRI is advised. If there is concern about radiation exposure at CT, MRI may be used instead of CT in selected instances.

Endoscopy, Laparoscopy: The utilization of these techniques for objective tumor evaluation is not advised. However, such techniques may be useful to confirm complete pathological response when biopsies are obtained or to determine relapse in trials where recurrence following complete response (CR) or surgical resection is an endpoint.

Tumor markers: Tumor markers alone cannot be used to assess response. If markers are initially above the upper normal limit, they must normalize for a patient to be considered in complete clinical response. Specific guidelines for both CA-125 response (in recurrent ovarian cancer) and PSA response (in recurrent prostate cancer) have been published [*JNCI* 96:487-488, 2004; *J Clin Oncol* 17, 3461-3467, 1999; *J Clin Oncol* 26:1148-1159, 2008]. In addition, the Gynecologic Cancer Intergroup has developed CA-125 progression criteria which are to be integrated with objective tumor assessment for use in first-line trials in ovarian cancer [*JNCI* 92:1534-1535, 2000].

Cytology, Histology: These techniques can be used to differentiate between partial responses (PR) and complete responses (CR) in rare cases (e.g., residual lesions in tumor types, such as germ cell tumors, where known residual benign tumors can remain).

The cytological confirmation of the neoplastic origin of any effusion that appears or worsens during treatment when the measurable tumor has met criteria for response or stable disease is mandatory to differentiate between response or stable disease (an effusion may be a side effect of the treatment) and progressive disease.

FDG-PET: While FDG-PET response assessments need additional study, it is sometimes reasonable to incorporate the use of FDG-PET scanning to complement CT scanning in assessment of progression (particularly possible 'new' disease). New lesions on the basis of FDG-PET imaging can be identified according to the following algorithm:

Negative FDG-PET at baseline, with a positive FDG-PET at follow-up is a sign of PD based on a new lesion.

No FDG-PET at baseline and a positive FDG-PET at follow-up: If the positive FDG-PET at follow-up corresponds to a new site of disease confirmed by CT, this is PD. If the positive FDG-PET at follow-up is not confirmed as a new site of disease on CT, additional follow-up CT scans are needed to determine if there is truly progression occurring at that site (if so, the date of PD will be the date of the initial abnormal FDG-PET scan). If the positive FDG-PET at follow-up corresponds to a pre-existing site of disease on CT that is not progressing on the basis of the anatomic images, this is not PD.

FDG-PET may be used to upgrade a response to a CR in a manner similar to a biopsy in cases where a residual radiographic abnormality is thought to represent fibrosis or scarring. The use of FDG-PET in this circumstance should be prospectively described in the protocol and supported by disease-specific medical literature for the indication. However, it must be acknowledged that both approaches may lead to false positive CR due to limitations of FDG-PET and biopsy resolution/sensitivity.

Note: A 'positive' FDG-PET scan lesion means one which is FDG avid with an uptake greater than twice that of the surrounding tissue on the attenuation corrected image.

Response Criteria

Evaluation of Target Lesions

Complete Response (CR): Disappearance of all target lesions. Any pathological lymph nodes (whether target or non-target) must have reduction in short axis to <10 mm.

Partial Response (PR): At least a 30% decrease in the sum of the diameters of target lesions, taking as reference the baseline sum diameters

Progressive Disease (PD): At least a 20% increase in the sum of the diameters of target lesions, taking as reference the smallest sum on study (this includes the baseline sum if that is the smallest on study). In addition to the relative increase of 20%, the sum must also demonstrate an absolute increase of at least 5 mm. (Note: the appearance of one or more new lesions is also considered progressions).

Stable Disease (SD): Neither sufficient shrinkage to qualify for PR nor sufficient increase to qualify for PD, taking as reference the smallest sum diameters while on study

Evaluation of Non-Target Lesions

Complete Response (CR): Disappearance of all non-target lesions and normalization of tumor marker level. All lymph nodes must be non-pathological in size (<10 mm short axis)

Note: If tumor markers are initially above the upper normal limit, they must normalize for a patient to be considered in complete clinical response.

Non-CR/Non-PD: Persistence of one or more non-target lesion(s) and/or maintenance of tumor marker level above the normal limits

Progressive Disease (PD): Appearance of one or more new lesions and/or *unequivocal progression* of existing non-target lesions. *Unequivocal progression* should not normally trump target lesion status. It must be representative of overall disease status change, not a single lesion increase.

Although a clear progression of “non-target” lesions only is exceptional, the opinion of the treating physician should prevail in such circumstances, and the progression status should be confirmed at a later time by the review panel (or Principal Investigator).

Evaluation of Best Overall Response

The best overall response is the best response recorded from the start of the treatment until disease progression/recurrence (taking as reference for progressive disease the smallest measurements recorded since the treatment started). The patient's best response assignment will depend on the achievement of both measurement and confirmation criteria.

For Patients with Measurable Disease (i.e., Target Disease)

Target Lesions	Non-Target Lesions	New Lesions	Overall Response	Best Overall Response when Confirmation is Required*
CR	CR	No	CR	≥ 4 wks. Confirmation**
CR	Non-CR/Non-PD	No	PR	≥ 4 wks. Confirmation**
CR	Not evaluated	No	PR	
PR	Non-CR/Non-PD/not evaluated	No	PR	
SD	Non-CR/Non-PD/not evaluated	No	SD	documented at least once ≥ 4 wks. from baseline**
PD	Any	Yes or No	PD	no prior SD, PR or CR
Any	PD***	Yes or No	PD	
Any	Any	Yes	PD	

* See RECIST 1.1 manuscript for further details on what is evidence of a new lesion.
** Only for non-randomized trials with response as primary endpoint.
*** In exceptional circumstances, unequivocal progression in non-target lesions may be accepted as disease progression.

Note: Patients with a global deterioration of health status requiring discontinuation of treatment without objective evidence of disease progression at that time should be reported as "*symptomatic deterioration*." Every effort should be made to document the objective progression even after discontinuation of treatment.

For Patients with Non-Measurable Disease (i.e., Non-Target Disease)

Non-Target Lesions	New Lesions	Overall Response
CR	No	CR
Non-CR/non-PD	No	Non-CR/non-PD*
Not all evaluated	No	not evaluated
Unequivocal PD	Yes or No	PD
Any	Yes	PD

* 'Non-CR/non-PD' is preferred over 'stable disease' for non-target disease since SD is increasingly used as an endpoint for assessment of efficacy in some trials so to assign this category when no lesions can be measured is not advised

Duration of Response

Duration of overall response: The duration of overall response is measured from the time measurement criteria are met for CR or PR (whichever is first recorded) until the first date that recurrent or progressive disease is objectively documented (taking as reference for progressive disease the smallest measurements recorded since the treatment started).

The duration of overall CR is measured from the time measurement criteria are first met for CR until the first date that progressive disease is objectively documented.

Duration of stable disease: Stable disease is measured from the start of the treatment until the criteria for progression are met, taking as reference the smallest measurements recorded since the treatment started, including the baseline measurements.

Progression-Free Survival

Progression-free survival (PFS) is defined as the duration of time from start of treatment to time of progression or death, whichever occurs first.

Duration of Disease Control

If an intermittent oxaliplatin strategy is chosen, the duration of disease control will be measured. Duration of disease control (DDC) is defined as the addition of the initial PFS and the PFS of the reintroduction, except in case of progression at the first evaluation after FOLFOX reintroduction [79, 80].

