6.5.2 FOLFOX

Patients will be treated with modified FOLFOX6 according to the following initial schedule for cycle 1. Cycle length is defined as 14 days. Modifications to cycle 1 treatment (other than oxaliplatin dose) may be allowed, but discussion with the primary investigator is required. Modifications to dosing beyond cycle 1 are at the discretion of the treating investigator according to usual medical practice.

Table 4. Modified FOLFOX6 Chemotherapy Regimen

Agent	Dose	Route	Day	Schedule
Leucovorin	400 mg/m ²	IV	1	Every 14 days
Calcium*				
5-FU	400 mg/m ²	Bolus IV	1	Every 14 days
Oxaliplatin	85 mg/m ²	IV over 2 hours	1	Every 14 days
5-FU	2400 mg/m ²	IV over 46-48 hours via ambulatory infusion pump	1-2	Every 14 days

*In the event of a leucovorin calcium shortage, the dosage may be reduced to 20 mg/m² or 200 mg/m² racemic levoleucovorin may be substituted. Leucovorin may be infused concurrently with oxaliplatin (via separate infusion lines).

** Note during cycle 1 only, Oxaliplatin infusion will contain [¹⁴C]Oxaliplatin Microdose as described in section 6.4.1

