7.3 Efficacy Assessments

For the purposes of this study, screening tumor assessments using CT of the chest/abdomen/pelvis and other areas of known disease or newly suspected disease should be performed within 28 days prior to registration. Scans of the abdomen, pelvis and other areas of the body may be done with MRI instead of CT, but evaluation of the chest should be done with CT. CT scans should be performed with iodinated IV contrast and MRI scans with IV gadolinium chelate unless there is a medical contraindication to contrast. If iodinated IV contrast is contraindicated, chest CT should be done without IV contrast. The CT component of a combined PET/CT may be used as long as the slice thickness is < 5 mm.

For the purposes of this study, patients with radiographically measurable disease at baseline should be re-evaluated for response every 8 weeks (+/- 1 week) for 6 months and then every 12 weeks (+/- 2 weeks) thereafter. The interval in imaging may be changed after discussion with the principal investigator. Response and progression will be evaluated in this study using the international criteria proposed by the revised Response Evaluation Criteria in Solid Tumors (RECIST) guideline (version 1.1) [Eur J Ca 45:228-247, 2009]. Changes in the largest diameter (unidimensional measurement) of the tumor lesions and the shortest diameter in the case of malignant lymph nodes are used in the RECIST criteria. Please see **Appendix C** for RECIST 1.1 criteria.

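### Patients who die or deteriorate before any tumour re-evaluation are left out of the adduct-response comparison instead of being counted as non-responders

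*Combined protocol and SAP*

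**What the plan says.** Appendix C limits objective response to patients with measurable disease at baseline who have had a first cycle of FOLFOX and "have had their disease re-evaluated will be considered evaluable for response". It names one exception: "Patients who exhibit objective disease progression prior to the end of cycle 1 will also be considered evaluable". Section 6.5.2 fixes the window this covers: "Cycle length is defined as 14 days". Under section 7.3, patients with measurable disease "should be re-evaluated for response every 8 weeks (+/- 1 week) for 6 months", then every 12 weeks.

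For clinical decline, the note under Best Overall Response in Appendix C takes "Patients with a global deterioration of health status requiring discontinuation of treatment without objective evidence of disease progression at that time" and has them reported as symptomatic deterioration. It adds: "Every effort should be made to document the objective progression even after discontinuation of treatment". It does not say whether that label counts as progression or as non-response, and it does not mention death before re-evaluation.

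Endpoint 8.2.2.3 (adducts against tumour response) and section 11.2.2.3 both send response to Appendix C. Neither gives a denominator of all treated patients. Section 11.2.2.3 counts death from any cause as a PFS event, and PFS feeds DDC in endpoint 8.2.2.4. Section 8.1 replaces patients only for a missed microdose or too few blood samples, so a missing tumour assessment does not trigger replacement.

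**The concern.** Section 11.2.2.3 hypothesizes that more DNA repair goes with non-response. Patients who fail before any tumour assessment are potentially the most informative non-responders. Their adduct samples already exist, because the last draw in Table 3 is at 48 hours of cycle 1. Under the Appendix C rule, whether those data enter the response comparison depends on the patient's outcome.

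Two things are at stake. The response rate rises whenever such a patient is dropped and there is at least one responder. The contrast in adducts between responders and non-responders may also be distorted. Section 11.2.1 says the adduct data will help decide the assay's future, so the comparison has some consequence even though section 11.2.2 calls it hypothesis generating.

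**Working it through.** **The plan's own figure.** The documents give no figure for the adduct-response comparison. The only sample size is 6, in section 11.3, set for the PK ratio. Take the stated CV range as the CV of the ratio, SD of the log ratio = √ln(1+CV²), a true ratio of 1, and 80% probability that the 95% interval lies within 0.5 to 2:

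- CV 0.3: SD 0.294, 5 patients needed
- CV 0.4: SD 0.385, 6 patients needed
- CV 0.5: SD 0.472, 8 patients needed

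Six is reproduced at the middle of the range. This point does not depend on that figure; 6 is used below only as the cohort size.

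**The uncovered window.** Assume the 8 weeks run from the start of FOLFOX, since section 7.3 does not state the origin. The first assessment falls at 8 × 7 = 56 days (49 to 63 with the tolerance). The exception ends at day 14. The gap is 56 − 14 = 42 days, or 6 weeks (35 to 49 days with the tolerance). Death without documented progression is uncovered from the first day of cycle 1, because the exception names only objective progression.

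**How each case is handled before the first scheduled assessment:**

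| Event | Endpoint 8.2.2.3 (response) | PFS/DDC (8.2.2.4) |
|---|---|---|
| Objective progression in cycle 1 | Counted | Event |
| Any re-evaluation, then death | Counted, if the first cycle was received | Event |
| Deterioration, progression later documented | Counted, if the first cycle was received | Event |
| Deterioration, no re-evaluation | Labelled, not assigned to non-response | Event at a later death |
| Death, no re-evaluation | Absent | Event |

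**Response rate.** With N patients with measurable disease, r responders and k early losses, the full rate is r/N and the Appendix C rate is r/(N − k). The second is larger whenever r and k are both at least 1. Assuming N = 6:

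- r = 2, k = 1: 2/6 = 33.3% becomes 2/5 = 40.0%
- r = 2, k = 2: 2/6 = 33.3% becomes 2/4 = 50.0%
- r = 3, k = 1: 3/6 = 50.0% becomes 3/5 = 60.0%

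N = 6 is itself an assumption, because section 4.1 does not require measurable disease.

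**Chance of at least one loss among 6.** This is 1 − (1 − q)⁶, where q is an assumed loss rate: 11% at q = 2%, 26% at 5%, 47% at 10%, 74% at 20%.

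**Adduct difference.** Simulation of 1,000,000 patients: adduct level A is standard normal; outcome Y = bA + standard normal error; the top 46% on Y respond (an assumption, using the figure for BSA-dosed FOLFOX patients in section 2.5); the lowest fraction q on Y is lost. Mean adduct difference, responders minus non-responders:

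| b | Nobody lost | q = 5% | q = 10% | q = 20% |
|---|---|---|---|---|
| 0.5 | 0.712 | 0.652 (−8%) | 0.609 (−15%) | 0.538 (−24%) |
| 1.0 | 1.126 | 1.029 (−9%) | 0.961 (−15%) | 0.849 (−25%) |

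With b = 0, or with losses random among non-responders, the difference is essentially unchanged. These are expected values; in about 6 patients chance variation will be far larger.

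**The case against.** - **Re-evaluated is wider than re-imaged.** Appendix C accepts caliper measurement of superficial lesions, and section 7.3 lets the imaging interval change after discussion with the principal investigator. A reader might infer that anyone without the 8-week scan is lost. The text does not support that: any earlier re-evaluation keeps the patient in. This stands and narrows the gap.
- **Deterioration is partly handled.** The instruction to document progression after stopping will recover some patients. It cannot help after an early death, and the label is still not tied to non-response.
- **Early losses need not occur.** A reader might infer that they are to be expected, since section 4.1 admits performance status 2, pancreatic cancer and heavily pretreated patients. The same section asks for an expected survival of 3 months, which is beyond the first assessment, and no loss rate is given. Such losses are plausible, no more.
- **The rule does not favour the assay.** A reader might infer that it would manufacture a positive biomarker result. It would not: bias in the comparison needs loss related to adducts or repair, and its likely direction is then toward no association.
- **Two endpoints, two measures.** Counting death in PFS but not in tumour response is not in itself a contradiction, and early deaths do reach endpoint 8.2.2.4. That limits the harm but leaves 8.2.2.3 selected by outcome.
- **The remedy can misclassify.** Counting every death as non-response labels toxic or unrelated deaths as resistance. This is fair, and is why both tables are needed.

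**Conclusion.** The point holds in limited form. As written, the rule removes from the adduct-response comparison any patient with measurable disease who dies, or stops for symptomatic deterioration, without any re-evaluation. When that happens and there is a responder, the response rate is overstated by simple arithmetic: by 6.7 points for one loss among 6 with 2 responders, and by 10 points with 3 responders. How often it will happen cannot be derived from the documents.

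Bias in the adduct comparison is conditional. Under the assumed model, with the worst outcomes lost and adducts predicting outcome, the difference shrinks by about 8% to 25% for losses of 5% to 20%. Without a link between loss and adducts there is none. The impact is confined to one descriptive secondary endpoint. The primary PK endpoint is unaffected.

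**What to change.** In Appendix C and section 11.2.2.3:

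1. Define the response set as every patient evaluable under section 8.1 who has measurable disease at baseline and starts FOLFOX. Tying it to section 8.1 keeps patients replaced for missing microdoses or samples out of the table.
2. Class death, or stopping for symptomatic deterioration, before any re-evaluation as non-response.
3. Identify deaths clearly unrelated to the cancer.
4. Show the re-evaluated-only table alongside as a sensitivity analysis.

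This is a change of wording and needs no new data. The costs are a somewhat lower reported response rate when such losses occur, and possible misclassification of non-cancer deaths, which the second table makes visible. The change should be made before outcomes are known, because a single patient can move the rate by 7 to 10 points in these examples.
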